#### 7.1.2 Selection of Data for Baseline

The baseline value will be chosen based on the rules specified below, unless otherwise specified.

## 7.1.2.1 Measurements Without a Source Recording Measurement Time Point

The baseline value will be the last non-missing and evaluable value prior to or on Study Day 1.

If multiple non-missing and evaluable records occur on the same day that is closest to Study Day 1 or on Study Day 1:

- For continuous measurements other than laboratory and PD biomarker data, the best of these records will be considered the baseline value.
- For continuous measurements for laboratory and PD biomarker data, the average of these records will be considered the baseline value.
- For categorical measurements regardless the type of endpoints (not applicable to categorical measurements derived from continuous measurements), the record with the lowest severity will be considered the baseline value, for example:
  - Lower grade severity will be selected over higher grade severity for toxicity grades or severity;
  - o "normal" will be selected over "low" and "high" for a test or exam with those categories;
  - o "normal" will be selected over "abnormal" for a test or exam with those two categories;
  - o "negative" will be selected over "positive" for a test or exam with those two categories.

For participants who didn't have Study Day 1 (i.e., never received study drug administration), their last data collected at the nominal visit of Screening or "Week 01 D01" (for cases when the extension of screening period was approved by the Sponsor) will be used as the baseline values if needed (e.g., summaries of Demographics and Baseline Characteristics on All Randomized Set).

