#### 7.1.2.2 Measurements With a Source Recording Measurement Time Point

For measurements that have a source recording the measurement time point (e.g., the measurement time point of vital signs and ECG data are recorded on the corresponding electronic CRF), the baseline value will be the last non-missing and evaluable value prior to Study Day 1, or the last non-missing and evaluable value with "predose", missing, or "not applicable" (i.e., excluding value collected post infusion)" as the measurement time point (as recorded in the source data) on Study Day 1. Non-missing values with "post infusion" (or containing "end of infusion" (EOI)) as the measurement time point (as recorded in the source data) on Study Day 1 will not be considered candidates for the baseline value and will be assigned the analysis visit "Day 1 Postdose" (Table 7-5, Table 7-6 and Table 7-8) when applicable.

If multiple non-missing and evaluable records occur on the same day that is closest to Study Day 1 (not on Study Day 1), or on Study Day 1 and all with "predose", missing, or "not applicable" as the measurement time point:

- For continuous measurements, the average of these values will be considered the baseline value.
- For categorical measurements (not applicable to categorical measurements derived from continuous measurements), the record with the lowest severity will be considered the baseline

Protocol No. AL002-2 Last Revision Date: 12 Aug 2025

value (e.g., "abnormal not clinically significant" will be selected over "abnormal clinically significant").

For participants who didn't have Study Day 1 (i.e., never received study drug administration), their last data collected at the nominal visit of Screening, "Predose Baseline", or "Week 01 D01" will be used as the baseline values if needed.

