## 7.1.3 Selection of Data in the Event of Multiple Records in a Post-Baseline Analysis Visit Window

## 7.1.3.1 Efficacy Data

#### For non-composite efficacy endpoints:

If multiple valid, non-missing efficacy records exist in a post-baseline analysis visit window, records will be chosen based on the following rules if a single value is needed, unless otherwise specified:

- The record closest to the target day (in terms of days) for that visit will be selected.
- If there are multiple records that are equidistant from the target day (in terms of days), the later record will be selected.
- If there are multiple records on the same day and the chronological order (in terms of day and time) can be determined (e.g., more than one record with time known on the same day), the latest record will be selected.
- If there are multiple records on the same day and the chronological order cannot be determined (e.g., more than one record on the same day with time missing), the worst record will be selected.

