#### 7.1.3.2 Safety and PD Biomarker Data

Depending on the statistical analysis method, a single value may be required for each analysis visit window (e.g., CFB by visit usually requires a single value), except for ">90 Days Post Last Dose" analysis visit window.

For safety data, if multiple valid, non-missing, continuous records exist in a post-baseline analysis visit window, records will be chosen based on the following rules if a single value is needed, unless otherwise specified:

- The record closest to the target day (in terms of days) for that visit will be selected.
- If there are multiple records that are equidistant from the target day (in terms of days), the later record will be selected.
- If there are multiple records on the same day (regardless of time), the average value will be taken.

For exploratory PD biomarker data, if multiple valid, non-missing, continuous records exist in a post-baseline analysis visit window, then the average value of these records will be taken.

For safety and exploratory PD biomarker data, if multiple valid, non-missing, categorical records exist in a post-baseline analysis visit window (not applicable to categorical measurements derived from continuous measurements), records will be chosen based on the following rules if a single value is needed, unless otherwise specified:

- The record closest to the target day for that visit (in terms of days) will be selected.
- If there are multiple records that are equidistant from the target day (in terms of days), the later record will be selected.
- If there are multiple records on the same day, the record with the worst severity will be selected, for example:
  - o higher grade severity will be selected over lower grade severity for toxicity grades;

Protocol No. AL002-2 Last Revision Date: 12 Aug 2025

- o "low" or "high" will be selected over "normal" for a test or exam with those categories;
- o "abnormal" will be selected over "normal" for a test or exam with those two categories;
- o "positive" will be selected over "negative" for a test or exam with those two categories.

For those categorical measurements derived from continuous measurements, if multiple valid, non-missing, continuous records exist in an analysis visit window, the rules for selecting a single value for continuous measurements apply first, then the corresponding categorical measurements will be derived based on the single selected continuous measurements.

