## 7.1.4.1.2 Handling of Other Special Characters

Non-PK data that are continuous in nature but have a "x - y" interval value will be imputed as best of "x - y" for baseline and worst of "x - y" for post-baseline as their continuous numeric value, if needed for calculating summary statistics.

Non-PK data that are continuous in nature but have "None" representing zero will be assigned 0, if needed for calculating summary statistics.

Protocol No. AL002-2 Last Revision Date: 12 Aug 2025

Non-PK data that are continuous in nature but have "ND (not done)", "QNS (quantity not sufficient)", "NR (no result(s))", or "Non-evaluable" representing non-valuable or missing value will be assigned missing, if needed for calculating summary statistics.

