## 7.5.5 Electrocardiogram (ECG)

Actual results and CFB values for the average of triplicate 12-lead ECGs (i.e., heart rate (beats/min), RR Interval (msec), QRS Duration (msec), QTcF Interval (msec)) will be summarized descriptively for each visit (refer to Table 7-5 for analysis visit window definition) and separated by predose and post-infusion (refer to Section 7.1.4.2 for handling of predose, post-infusion and "Not Applicable") per each visit. In addition, shift tables from baseline to post-baseline in the Investigator's overall interpretation of the ECG as indicated on the ECG electronic CRF will be provided for each visit. The summary will be separated by measurement time point (predose and post-infusion) per visit. Selection of data in the event of multiple records in an analysis visit window is specified in Section 7.1.3.2, separately for measurement time point (predose, post-infusion, and not applicable).

For the QTcF parameter as collected on the ECG electronic CRF, the number and percentage of participants in each criterion below will be summarized separated by measurement time point (predose and post-infusion) per visit and overall during the treatment period. For overall, the record with the most severe finding will be selected for a participant.

- Of the absolute QTcF interval prolongation:
  - $\circ$  > 450 msec.
  - $\circ$  > 480 msec,
  - $\circ$  > 500 msec.
- Of the CFBs in OTcF interval:
  - $\circ$  > 30 msec,
  - $\circ$  > 60 msec.

The number and percentage of participants in each criterion below (Table 7-23) will be summarized separated by measurement time point (predose and post-infusion) per visit and overall during the treatment period. For overall, the record with the most severe finding will be selected for a participant.

Table 7-23. ECG Parameter Criteria

ECG Parameter	Low Criteria	High Criteria
Heart Rate	< 50 beats/min	> 100 beats/min
RR Interval	< 600 msec	> 1200 msec
QRS Duration	< 60 msec	≥ 120 msec

All ECG data as collected on the ECG electronic CRF will be listed.

The same analyses described above will also be performed for the centrally read ECGs, when applicable.

Protocol No. AL002-2 Last Revision Date: 12 Aug 2025

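### SAP conventions take the best value at baseline and a worse or neutral one afterwards, for interval results and some same-day ties, so an unchanged participant can appear to worsen

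*SAP*

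**What the plan says.** Three parts of SAP 7.1 choose or impute a value differently before and after the first dose.

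- **Interval results (7.1.4.1.2).** For non-PK data that are continuous in nature, the "interval value will be imputed as best of 'x - y' for baseline and worst of 'x - y' for post-baseline". This applies where a number is needed for summary statistics. SAP 7.5.4.1 summarises actual values and change from baseline for continuous laboratory parameters.
- **Same-day categorical records.** At baseline (7.1.2.1 and 7.1.2.2), "the record with the lowest severity will be considered the baseline" value. Post-baseline (7.1.3.2): "If there are multiple records on the same day, the record with the worst severity will be selected". Categories derived from a continuous measurement are exempt on both sides.
- **Same-day continuous records with no recorded time point, other than laboratory and biomarker data.** This class appears to include the clinical outcome assessments (COAs). At baseline (7.1.2.1), "the best of these records will be considered the baseline value". For post-baseline efficacy data (7.1.3.1), the record closest to the target day is used, then the later one, then the latest on the same day. Only when same-day order cannot be determined does the SAP say "the worst record will be selected".

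Other data are treated evenly. For laboratory and biomarker duplicates at baseline, the SAP says: "For continuous measurements for laboratory and PD biomarker data, the average of these records will be considered the baseline value". Section 7.1.2.2 averages continuous ECG and vital-sign values at baseline. Section 7.1.3.2 averages same-day continuous safety values, and all biomarker values in a window, after baseline. Section 7.5.5 analyses the mean of the ECG triplicate.

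SAP 7.4 sends multiple efficacy values to 7.1.3.2, the safety and biomarker rule, although the efficacy rule is in 7.1.3.1.

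**The concern.** A change from baseline should be zero on average for a participant who has not changed. A rule that picks the favourable value first and an unfavourable one later breaks this, and the error is always toward worsening. The SAP gives no reason for treating the two sides differently. A cautious reading of post-baseline safety data may justify taking the worst value there, but it does not require taking the best value at baseline. For COAs there is no safety argument at all.

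What is at stake is the credibility of within-arm change summaries and shift tables. For the COAs there is also a small distortion of the percent-reduction estimate, because a constant added to every arm's decline does not cancel out of a ratio.

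**Working it through.** The plan states no figure for the size or frequency of this effect, so there is none to reproduce. The check sets the rules side by side and then sizes each for an unchanged participant.

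**Rules side by side**

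| Data | Baseline | Post-baseline | Even-handed? |
|---|---|---|---|
| Interval value of a continuous non-PK result | best end | worst end | No |
| Categorical, same day | lowest severity | worst severity | No |
| COA, same day | best | latest; worst if order unknown | No |
| Numeric laboratory, same day | average | average | Yes |
| Numeric ECG and vital signs, same day | average | average | Yes |

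**Interval values.** Where lower is better, baseline = x and post-baseline = y, so change = y − x for an identical result. The intervals here are my examples; the documents contain none.
- 0-2 at both visits: 2 − 0 = +2
- 3-5 at both visits: 5 − 3 = +2
- 6-10 at both visits: 10 − 6 = +4

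With the midpoint on both sides, change = (x + y)/2 − (x + y)/2 = 0. No duplicate record is needed for the artefact to arise.

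**Same-day COAs.** Assume two independent, normally distributed readings with the same mean and within-person SD s. The expected better-of-two lies s/√π = 0.56s on the good side of the mean.
- Best of two at baseline against one unselected later value (the latest-record rule): apparent worsening 0.56s.
- Best of two at baseline against worst of two later (order unknown): 2 × 0.564s = 1.13s.
- Average against average: 0.

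Simulation gave 0.563, 1.128 and 0.000 in units of s.

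For the proportional model in SAP 7.4.1.1, let the true placebo change at a visit be Δ, the true active-arm change be (1 − θ)Δ, and the average artefact be δ in every arm. The apparent proportional effect at that visit is

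1 − [(1 − θ)Δ + δ]/(Δ + δ) = θΔ/(Δ + δ),

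which is smaller than θ when θ, Δ and δ are positive. In the MMRM the difference between arms is (Δ + δ) − [(1 − θ)Δ + δ] = θΔ, so δ cancels there. Since δ is 0.56s to 1.13s multiplied by the share of participants with same-day duplicates, and the schedule has one CDR per visit, δ should be small.

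**Categorical records: which common rule?** Suppose three records are stored per time point, each independently abnormal with an assumed probability p = 0.10.
- Worst on both sides: P(abnormal) = 1 − 0.9³ = 0.271. False shifts each way are 0.271 × 0.729 = 19.8%, net zero.
- Majority on both sides: P(abnormal) = 3 × 0.01 × 0.9 + 0.001 = 0.028. False shifts each way are 0.028 × 0.972 = 2.7%, net zero.

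Both remove the tilt, but majority does so with far fewer false shifts.

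**The case against.** The strongest reply is that these are last-resort tie-breaks in descriptive outputs, applied identically in every arm with a concurrent placebo group. Most of that stands. No dose is favoured. The best-record rule at baseline has no general worst-record partner, because the worst is used for efficacy data only when order is unknown. The documents give no frequency for interval results. Urine microscopy, which I infer is a likely source, is done only after an abnormal dipstick.

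A reader might infer from the triplicate ECG design that the problem arises at every ECG visit. The documents do not support that. Numeric ECG parameters are averaged. SAP 7.5.5 tabulates the investigator's overall interpretation, and SAP 6.3.5 describes the investigator's assessment of the ECG in the singular. If one interpretation is stored per triplicate, there is nothing to select from. The baseline example in 7.1.2.2 uses ECG categories, but a same-day repeat ECG would explain it equally well. The eCRF is not in the documents.

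Nor can a size be put on it. If the three tracings agree completely on a share r of occasions and are otherwise independent, the net excess of worsening at p = 0.10 is (1 − r) × (0.271 − 0.001). That is 27.0, 13.5, 2.7 or 0 percentage points at r = 0, 0.5, 0.9 or 1. Tracings taken minutes apart in a resting participant are unlikely to be independent.

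The objection is also right that worst severity on both sides is a poor remedy. At p = 0.10 with independent tracings it gives 2 × 19.8% = about 39.5% false shifts in total, against about 27.1% under the current rule.

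What the objection does not answer is why the two sides differ at all. Placebo control protects the comparison, not the within-arm change.

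**Conclusion.** The point holds in limited form. For interval values the artefact is certain whenever such a result is summarised numerically: an unchanged result gives a worsening of y − x. For same-day categorical records the direction is certain, but the size depends on how many records exist and how well they agree. The ECG interpretation table is affected only if more than one interpretation is stored per time point, which the documents do not show. For COAs the shift is 0.56 to 1.13 within-person SD for an affected participant, under the normality and independence assumed above, and probably negligible on average. Its effect on the primary estimate would be a slight pull toward zero, against AL002.

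The documents do not support reading this as a frequent problem, as a distortion of numeric ECG or duplicate laboratory data, or as a bias toward any dose. It is worth correcting because the direction is built in, no rationale is given and the change is cheap. The cross-reference in SAP 7.4 is a separate, plain error: read literally, it leaves open whether same-day efficacy values are averaged or the latest is taken.

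**What to change.** Apply one rule on both sides of baseline.

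- **7.1.4.1.2:** impute an interval value as its midpoint at every visit. This also removes the need to define which end is best for analytes that can be abnormal in either direction.
- **7.1.2.1 and 7.1.3.1:** for same-day COAs, take the latest by time at both baseline (before dosing) and post-baseline; where order is unknown, take the average. Apply the same change to the component-selection rule for the composite endpoints, which also falls back on the worst value.
- **7.1.2.1, 7.1.2.2 and 7.1.3.2:** state one severity rule for same-day categorical records at all visits. For triplicate ECGs, use the single overall interpretation if that is what the eCRF holds, otherwise the majority category. Do not use worst on both sides.
- **7.4:** change the cross-reference for multiple efficacy values from 7.1.3.2 to 7.1.3.1.

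The cost is a few lines of SAP text and a small programming change before database lock. No new data are needed. Counting the interval results and same-day duplicates in blinded data would show how much the change matters.

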#### 7.1.2.2 Measurements With a Source Recording Measurement Time Point

For measurements that have a source recording the measurement time point (e.g., the measurement time point of vital signs and ECG data are recorded on the corresponding electronic CRF), the baseline value will be the last non-missing and evaluable value prior to Study Day 1, or the last non-missing and evaluable value with "predose", missing, or "not applicable" (i.e., excluding value collected post infusion)" as the measurement time point (as recorded in the source data) on Study Day 1. Non-missing values with "post infusion" (or containing "end of infusion" (EOI)) as the measurement time point (as recorded in the source data) on Study Day 1 will not be considered candidates for the baseline value and will be assigned the analysis visit "Day 1 Postdose" (Table 7-5, Table 7-6 and Table 7-8) when applicable.

If multiple non-missing and evaluable records occur on the same day that is closest to Study Day 1 (not on Study Day 1), or on Study Day 1 and all with "predose", missing, or "not applicable" as the measurement time point:

- For continuous measurements, the average of these values will be considered the baseline value.
- For categorical measurements (not applicable to categorical measurements derived from continuous measurements), the record with the lowest severity will be considered the baseline

Protocol No. AL002-2 Last Revision Date: 12 Aug 2025

value (e.g., "abnormal not clinically significant" will be selected over "abnormal clinically significant").

For participants who didn't have Study Day 1 (i.e., never received study drug administration), their last data collected at the nominal visit of Screening, "Predose Baseline", or "Week 01 D01" will be used as the baseline values if needed.

#### 7.1.2.3 Tau PET Measurement

Two definitions for baseline will be used for Tau PET (refer to Table 7-26 for analysis scope for PD biomarkers).

- *True baseline*: evaluable Tau PET scan result at Pre-dose Baseline visit prior to Study Day 1. If the Tau PET scan is not performed at the Pre-dose Baseline visit, then the baseline value is set to missing.
- Redefined baseline: evaluable Tau PET scan result at Pre-dose Baseline visit prior to Study Day 1
  if available or the first evaluable post-dose Tau PET scan result if pre-dose Tau PET scan is
  missing.

True baseline will be used in the main analyses for CFB. Redefined baseline will be used in the sensitivity analyses for CFB.

For participants who never received study drug administration, but were randomized, their data collected at the Screening visit will be used as the baseline value if needed (e.g., summaries of baseline characteristics on the ARS).

## 7.1.3 Selection of Data in the Event of Multiple Records in a Post-Baseline Analysis Visit Window

## 7.1.3.1 Efficacy Data

#### For non-composite efficacy endpoints:

If multiple valid, non-missing efficacy records exist in a post-baseline analysis visit window, records will be chosen based on the following rules if a single value is needed, unless otherwise specified:

- The record closest to the target day (in terms of days) for that visit will be selected.
- If there are multiple records that are equidistant from the target day (in terms of days), the later record will be selected.
- If there are multiple records on the same day and the chronological order (in terms of day and time) can be determined (e.g., more than one record with time known on the same day), the latest record will be selected.
- If there are multiple records on the same day and the chronological order cannot be determined (e.g., more than one record on the same day with time missing), the worst record will be selected.

#### For composite efficacy endpoints (ADCOMS and modified iADRS):

If all of the individual components have no more than one value on the same day, then the composite score is first calculated based on all the individual components (one per component) collected on the same

Protocol No. AL002-2 Last Revision Date: 12 Aug 2025

day. After the composite score is calculated, if multiple composite scores exist in a post-baseline analysis visit window, then:

- The record closest to the target day (in terms of days) for that visit will be selected.
- If there are multiple records that are equidistant from the target day (in terms of days), the later record will be selected.

If one or more individual components have multiple values on the same day, then the following rules of selection for those individual components apply first, followed by the rules above to calculate and select the composite score:

- If there are multiple values on the same day and the chronological order (in terms of day and time) can be determined (e.g., more than one record with time known on the same day), the latest record will be selected.
- If there are multiple values on the same day and the chronological order cannot be determined (e.g., more than one record on the same day with time missing), the record with the worst value will be selected.

